7.10. Safety Evaluation

All adverse events are collected throughout the duration of this study, starting from the time of signing the Informe Consent through study closure. Adverse Events will be recorded and reported according to local regulatory requirements. The current version of MedDRA coding will be used.

The following summary tables and supporting data listings:

Table 3.1.2 – Adverse Events by System Organ Class and Preferred Term – FAS

Table 3.1.3 – Adverse Events by System Organ Class, Preferred Term and Relationship to Bone Cement – FAS

Listing 2- Adverse Event – FAS

Listing 3- Adverse Event leading to death – FAS

Xpede Clinical Study

Statistical Analysis Plan

Version 1.0

Page 14 of 19

Medtronic

7.11. Health Outcomes Analyses

No health economic outcomes have been planned for this study.

7.12. Visit windows

The visit windows for this study were defined in the table below. The days should be counted from the day of the study procedure.

For endpoints which can be collected remotely and are filled by patient (e.g., NBS, SF-36, ODI questionnaires), follow-up visit should be performed as closely to the target day as possible (± 2 weeks are allowed for the last two follow up visits).

For the endpoints which require assessment on site and X-ray/MRI assessment (e.g., vertebral body angle and vertebral body height), the follow-up visits can be completed at any time during the visit window.

Visit name	Target day	Endpoints/assessments which can be done remotely	Endpoints/assessments which require on-site visit
Baseline and randomization	\leq Day 0		
Study Procedure	Day 0		
1 Day post-operative	Day 1	Day 1 – Day 7	Day 1 – Day 7
3 months postoperative	Day 90	Day 8 – Day 135	Day 8 – Day 135
6 months postoperative	Day 180	Day 136 – Day -365	Day 136 – Day 365

Note: In case of missing assessments within the visit windows, clinical judgment could lead to acceptance/rejection of some measurements out of windows.

7.13. Changes to Planned Analysis

The analysis described in the CIP could differ from that presented in this SAP due to data availability. Any deviation from the original statistical plan will be described and justified in the final report, as appropriate.

8. Validation Requirements

All collected data will be reviewed for completeness, correctness and consistency. In case of issues, queries will be sent to the investigator to complete, correct or comment the data. To ensure the quality of the results provided for the study in the form of tables, listings and figures, and the derived datasets the following processes are used:

- Statistical programming and analysis will be done by qualified programmer(s) and statistician(s) following applicable procedures and best practices.
- The derived datasets will be validated by a second programmer or statistician.
- The tables will be validated by a second programmer or statistician.
- Statistical results will be reviewed and confirmed by a second statistician.

The entire set of tables, listings, and figures (TLF) will be 100% checked for accuracy, completeness, and consistency prior to inclusion in the final clinical study report. Double programming will be implemented for both Datasets and TLFs.

9. References

1. <http://www.consort-statement.org/>
2. Jan Van Meirhaeghe, Leonard Bastian, Steven Boonen, Jonas Ranstam, John B. Tillman, Douglas Wardlaw, on behalf of the FREE investigators. A Randomized Trial of Balloon Kyphoplasty and Nonsurgical Management for Treating Acute Vertebral Compression Fractures. SPINE Volume 38, Number 12, pp 971–983. ©2013, Lippincott Williams & Wilkins
3. James Berenson, Robert Pflugmacher, Peter Jarzem, Jeffrey Zonder, Kenneth Schechtman, John B Tillman, Leonard Bastian, Talat Ashraf, Frank Vrionis, for the Cancer Patient Fracture Evaluation (CAFE) Investigators. Balloon kyphoplasty versus non-surgical fracture management for treatment of painful vertebral body compression fractures in patients with cancer: a multicentre, randomised controlled trial. Lancet Oncol 2011; 12: 225–35.

10. Statistical Appendices

10.1. Mock TLFs

Please refer to a separate TLF mock-up.

10.2. Graphical explanation for primary endpoint

The primary endpoint will be presented as the low box on the right of the example figure below:

[figure not shown]
Xpede Clinical Study

Statistical Analysis Plan

Version 1.0

Page 16 of 19

Medtronic

10.3. Secondary Endpoint calculation

10.3.1. Vertebral Body Height Restoration

The vertebral body height restoration will be expressed as Absolute Height Restored (AHR) for anterior, mid and posterior defined as:

AHRA: $Ha_{\text{post-treatment}} - Ha_{\text{at treatment}}$: where the anterior (Ha) vertebral body height is measured in millimeters (mm)

AHRM: $Hm_{\text{post-treatment}} - Hm_{\text{at treatment}}$: where the mid (Hm) vertebral body height is measured in millimeters (mm)

AHRP: $Hp_{\text{post-treatment}} - Hp_{\text{at treatment}}$: where the posterior (Hp) vertebral body height is measured in millimeters (mm)

Note that *change from baseline treatment to post-treatment* will be calculated as the difference between post-treatment in treated level and the baseline treatment in nearest superior, adjacent, non-fractured level.

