7.4. Intended Population

KYPHON™ Xpede™ Bone Cement is indicated for the treatment of pathological fractures of the vertebral body due to osteoporosis, cancer, or benign lesions using a cementoplasty (i.e. kyphoplasty or vertebroplasty) procedure. It is also indicated for the fixation of pathological fractures of the sacral vertebral body or ala using sacral vertebroplasty or sacroplasty. Cancer includes multiple myeloma and metastatic lesions, including those arising from breast or lung cancer, or lymphoma. Benign lesions include hemangioma and giant cell tumor. Pathological fracture may include a symptomatic microfracture (as documented by appropriate imaging and/or presence of a lytic lesion) without obvious loss of vertebral body height.

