9.8. Radiography assessment

Radiological measurements will be made both by the blinded site personnel and by a centralized, independent radiologist (corelab).

A. Vertebral Body Height

Vertebral body height should be assessed at Pre-Operative, 1 days, 3-, 6-month.

Vertebral Body Height in the lateral projection will be measured at each treated vertebra as well as the next adjacent vertebrae (superior and inferior) without fracture and reported in millimeters. Vertebral Body Height is the distance between comparable points on the superior and inferior

endplates of the vertebral body at the posterior (Hp), midline (Hm) and anterior (Ha) locations as shown in Figure 3.

Notes about Adjacent Vertebral Body Height Measurements:

Note 1: The normal estimated pre-fracture height of the treated vertebra will be based on the average of the nearest adjacent non-fractured vertebrae (see Figure 4 below). The reviewer will record the level of the nearest non-fractured level superior to and inferior to the treated level.

Note 2: When L5 is the treated vertebra, the estimated pre-fracture (predicted) height of L5 will be based on L4 or the nearest superior non-fractured level. The height of S1 is not suitable as a predictor of the pre-fracture height of L5.

Note 3: The height of the nearest adjacent, non-fractured, vertebrae may be calculated at a single time point and used for all measurements at other time points. In general, the adjacent level vertebral heights will be obtained at the Pre-Operative time point from standing neutral lateral x-rays.

Note 4: In some cases, the superior or inferior adjacent vertebra may be poorly visualized at the Pre-Operative visit due to inadequate image quality. In this situation, the adjacent vertebra may be excluded from the analysis, or a subsequent visit, e.g. Post-Operative, may be used to obtain a reliable measurement of the adjacent vertebral body height.

- 1) Posterior height (Hp) is obtained by placing a vertical line along the dorsal surface of the vertebral body from the posterior point of the superior vertebral body endplate to the posterior point of the inferior endplate.

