7.9.2. Secondary Endpoints

The secondary endpoints include:

- Change of NRS score from baseline at 1 day and 3-month visit
- Change of ODI (see section 10.3 for details) from baseline at 1 day, 3-month visit and 6-month visit
- Change of SF-36 (see section 10.3 for details) from baseline at 1 day, 3-month visit and 6-month visit
- Change of Vertebral body height restoration (see section 10.3 for calculation) at 1 day and 3-month visit and 6-month visit
- Change of Vertebral body angle from baseline at 1 day, 3-month visit and 6-month visit

The analysis will use multiple data points per patient (1 day, 3 months, 6 months). Assuming not completely independence among measures within same patient the analysis will be performed by means of Generalized Estimating Equation (or mixed models for repeated measures) using patient as the subject ID. The model will have the NRS, ODI, SF-36 (PCS, MCS), height restoration and angle as dependent variables (for each model) and baseline value, arm as explanatory variables. All assumptions for regression models will be assessed by viewing plots of the residual values. Potential confounders could be included in the model to adjust estimates.

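### SAP 10.3.1 defines the secondary height-restoration endpoint in two incompatible ways, and one of them subtracts another vertebra's height and so does not measure height restored

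*SAP*

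**What the plan says.** SAP 7.9.2 lists one height endpoint: "Change of Vertebral body height restoration (see section 10.3 for calculation) at 1 day and 3-month visit and 6-month visit". The model there, a GEE or repeated-measures mixed model, takes "height restoration and angle as dependent variables (for each model) and baseline value, arm as explanatory variables".

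SAP 10.3.1 says that height restoration "will be expressed as Absolute Height Restored (AHR) for anterior, mid and posterior". Each of the three formulas (Ha, Hm, Hp) is post-treatment height minus height at treatment, in millimetres, and none names a vertebral level. A Note directly below says that the change from baseline to post-treatment "will be calculated as the difference between post-treatment in treated level and the baseline treatment in nearest superior, adjacent, non-fractured level". This is the only sentence in the section that says which vertebrae enter the subtraction.

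Protocol 9.8 has heights measured on the treated vertebra and on the adjacent unfractured ones, and fixes the time points: "Vertebral body height should be assessed at Pre-Operative, 1 days, 3-, 6-month". It gives the neighbours a specific purpose: "The normal estimated pre-fracture height of the treated vertebra will be based on the average of the nearest adjacent non-fractured vertebrae". For L5 only superior levels are used, and a poorly visualized neighbour may be left out or measured on a later film.

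**The concern.** The two rules in SAP 10.3.1 do not give the same variable. The formulas, read as the same vertebra before and after, measure the height gained. The Note measures how far the treated vertebra ends from an unfractured vertebra above it. Nothing in the SAP or protocol says which rule governs.

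Two programmers could each follow the text and derive different variables, although SAP section 8 relies on independent double programming for validation. If the Note is followed, the per-arm values at 1 day, 3 months and 6 months usually carry the wrong sign and the wrong meaning: a real gain appears as a loss, and complete restoration appears as zero.

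The ambiguity also reaches the model. The baseline value in SAP 7.9.2 could be the treated vertebra's pre-operative height or the neighbour's height.

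**Working it through.** The plan states no figure for this endpoint (no expected value, margin or sample size), so there is nothing to reproduce. The check is algebra on the two rules, followed by an illustration.

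**Notation.** P = height of the treated vertebra at a follow-up visit; B = its own pre-operative height; N = baseline height of the unfractured vertebra above it; D = N - B.

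**Identity.**
- Formula (same-vertebra reading): AHR = P - B.
- Note: P - N = (P - B) - (N - B) = AHR - D.

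The rules differ by exactly D for every vertebra at every visit, and agree only if D = 0. The Note value is negative whenever the treated vertebra ends below its neighbour, zero when it matches it, and positive when it ends above.

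**Illustration with assumed heights.** Take N = 25 mm and let r be the fraction of the loss regained. Then AHR = rD and Note = rD - D = -(1 - r)D.

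| D (mm) | r | AHR (mm) | Note (mm) |
|---|---|---|---|
| 8 | 0 | 0 | -8 |
| 8 | 0.25 | +2 | -6 |
| 8 | 0.50 | +4 | -4 |
| 8 | 0.75 | +6 | -2 |
| 8 | 1.00 | +8 | 0 |
| 8 | 1.125 | +9 | +1 |
| 2 | 0.50 | +1.0 | -1.0 |
| 5 | 0.50 | +2.5 | -2.5 |
| 10 | 0.50 | +5.0 | -5.0 |

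The first row and the r = 1.00 row show the problem most clearly. With nothing restored the Note reports -8 mm, and with everything restored it reports 0.

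**Little height loss.** Protocol 7.4 includes symptomatic microfractures "without obvious loss of vertebral body height". Suppose B = 24.5 and P = 24.7 mm, so AHR = +0.2 mm. The Note gives 24.7 - 24.0 = +0.7, 24.7 - 24.7 = 0, or 24.7 - 25.0 = -0.3 mm for neighbours of 24.0, 24.7 and 25.0 mm. The result then depends mainly on which neighbour the patient happens to have.

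**Effect on the comparison of arms.** Randomization makes the expected D equal in the two arms, so it cancels from the expected difference. A simulation (4,000 runs, 90 per arm) confirmed this. Its assumptions were: N with mean 25 and SD 2.5 mm; loss as the absolute value of a normal with mean 7 and SD 3 mm; 40% of the loss regained; residual SD 1.5 mm; a true arm difference of -0.5 mm; and one level per patient.

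| | Formula | Note |
|---|---|---|
| Control-arm mean (mm) | +2.8 | -4.2 |
| Arm difference, unadjusted (mm) | -0.51 | -0.49 |
| Empirical SE, unadjusted | 0.29 | 0.34 |
| Empirical SE, adjusted for B | 0.25 | 0.28 |

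Under these assumptions the per-arm mean changes sign, the arm difference stays close to the true value, and the Note loses some precision.

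**Against Protocol 9.8.** The Note is not the protocol's predicted height either. The protocol generally averages the nearest unfractured levels and uses superior levels only for L5; the Note uses the superior level throughout. It also has no rule for a superior neighbour that has been excluded for poor image quality.

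**The case against.** The strongest reply is that the contradiction is less firm than it looks, because the AHR formulas name no vertebra. The Note might supply the missing reference level, leaving one rule with a poor label. Or it might define a second quantity, since it is worded for change from baseline and not for AHR. Neither reading rescues the text. Under the first, the SAP still reports P - N as height restored, which is non-zero when nothing was restored and zero when everything was. Under the second, the SAP would need to say that there are two outputs, and 7.9.2 names one.

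Several narrower points do stand:
- All the millimetre figures are assumed; only the identity comes from the documents.
- Residual deficit is a loose name for the Note value, which can be zero or positive and is not measured against the protocol's predicted height.
- The time point is recoverable: Table 5 schedules X-rays at baseline and follow-up but not on the procedure day, so the reference film can only be the pre-operative one.
- Magnification adjustment is already required by Protocol 9.8.
- The doubt over the baseline covariate follows from the Note and is not a separate error.
- This is a secondary endpoint with no margin, stated hypothesis or sample size.

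**Conclusion.** The concern holds. SAP 10.3.1 contains two rules that differ by D and coincide only when the treated vertebra had the same height as its superior neighbour before treatment. The Note is the faulty text: what it computes is neither height restored nor a change from the treated vertebra's own baseline, and it conflicts with the use of adjacent levels in Protocol 9.8. This conclusion rests on the wording and the identity, not on the assumed heights. For assumed losses of 2 to 10 mm, half regained, the discrepancy is 2 to 10 mm and reverses the sign.

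The consequence is limited to the per-arm summaries of one secondary endpoint at three visits, some loss of precision, and an undefined covariate in its model. The sample size and the requirement that both co-primary endpoints (NRS and vertebral body angle) be met are untouched. It should be corrected before the endpoint is programmed, but it does not threaten the primary conclusion.

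**What to change.** In SAP 10.3.1, replace the Note with a single rule: height restored (Ha, Hm, Hp) is the height of the treated vertebra at the visit minus that same vertebra's pre-operative height, both adjusted for magnification as in Protocol 9.8. In the formulas, replace the reference to the time of treatment with the pre-operative baseline film. In SAP 7.9.2, state that the baseline value in the height model is the treated vertebra's pre-operative height.

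If a comparison with normal height is wanted, report it as a separate output labelled residual deficit, against the predicted height in Protocol 9.8 Notes 1 and 2. A percentage-restored measure is optional. It would need a minimum baseline loss stated in advance, because its denominator approaches zero when predicted and pre-operative heights are close.

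The cost is SAP wording and derivation code. Protocol 9.8 already collects the treated and adjacent heights, so no new data are needed.

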10.3.2. SF36

The SF-36 has eight scaled scores; the scores are weighted sums of the questions in each section. Scores range from 0 – 100, Lower scores = more disability, higher scores = less disability.

Xpede Clinical Study

Statistical Analysis Plan

Version 1.0

Page 17 of 19

Medtronic

It is composed by the following sections:

- Vitality
- Physical functioning
- Bodily pain
- General health perceptions
- Physical role functioning
- Emotional role functioning
- Social role functioning
- Mental health

The following link gives guidance:

https://www.rand.org/health-care/surveys_tools/mos/36-item-short-form/scoring.html

10.3.3. ODI

The Oswestry Disability Index (ODI) is one of the condition-specific questionnaires recommended for use with patients with back pain. It is composed by 10 section as follow:

Section 1: Pain Intensity

- I have no pain at the moment. [0 points]
- The pain is very mild at the moment. [1 point]
- The pain is moderate at the moment. [2 points]
- The pain is fairly severe at the moment. [3 points]
- The pain is very severe at the moment. [4 points]
- The pain is the worst imaginable at the moment. [5 points]

Section 2: Personal Care

- I can look after myself normally without causing extra pain. [0 points]
- I can look after myself normally but it is very painful. [1 point]
- It is painful to look after myself and I am slow and careful. [2 points]
- I need some help but manage most of my personal care. [3 points]
- I need help every day in most aspects of self care. [4 points]
- I do not get dressed, wash with difficulty and stay in bed. [5 points]

Section 3: Lifting

- I can lift heavy weights without extra pain. [0 points]
- I can lift heavy weights but it gives extra pain. [1 point]
- Pain prevents me from lifting heavy weights off the floor but I can manage if they are conveniently positioned, e.g. on a table. [2 points]
- Pain prevents me from lifting heavy weights but I can manage light to medium weights if they are conveniently positioned. [3 points]
- I can lift only very light weights. [4 points]
- I cannot lift or carry anything at all. [5 points]

Section 4: Walking

- Pain does not prevent me walking any distance. [0 points]
- Pain prevents me walking more than one mile. [1 point]
- Pain prevents me walking more than a quarter of a mile. [2 points]

Xpede Clinical Study

Statistical Analysis Plan

- Pain prevents me walking more than 100 yards. [3 points]
- I can only walk using a stick or crutches. [4 points]
- I am in bed most of the time and have to crawl to the toilet. [5 points]

Section 5: Sitting

- I can sit in any chair as long as I like. [0 points]
- I can sit in my favourite chair as long as I like. [1 point]
- Pain prevents me from sitting for more than 1 hour. [2 points]
- Pain prevents me from sitting for more than half an hour. [3 points]
- Pain prevents me from sitting for more than 10 minutes. [4 points]
- Pain prevents me from sitting at all. [5 points]

Section 6: Standing

- I can stand as long as I want without extra pain. [0 points]
- I can stand as long as I want but it gives me extra pain. [1 point]
- Pain prevents me from standing for more than 1 hour. [2 points]
- Pain prevents me from standing for more than half an hour. [3 points]
- Pain prevents me from standing for more than 10 minutes. [4 points]
- Pain prevents me from standing at all. [5 points]

Section 7: Sleeping

- My sleep is never disturbed by pain. [0 points]
- My sleep is occasionally disturbed by pain. [1 point]
- Because of pain I have less than 6 hours sleep. [2 points]
- Because of pain I have less than 4 hours sleep. [3 points]
- Because of pain I have less than 2 hours sleep. [4 points]
- Pain prevents me from sleeping at all. [5 points]

Section 8: Sex Life (if applicable)

- My sex life is normal and causes no extra pain. [0 points]
- My sex life is normal but causes some extra pain. [1 point]
- My sex life is nearly normal but is very painful. [2 points]
- My sex life is severely restricted by pain. [3 points]
- My sex life is nearly absent because of pain. [4 points]
- Pain prevents any sex life at all. [5 points]

Section 9: Social Life

- My social life is normal and causes me no extra pain. [0 points]
- My social life is normal but increases the degree of pain. [1 point]
- Pain has no significant effect on my social life apart from limiting my more energetic interests, e.g. sport, etc. [2 points]
- Pain has restricted my social life and I do not go out as often. [3 points]
- Pain has restricted social life to my home. [4 points]
- I have no social life because of pain. [5 points]

Section 10: Traveling

- I can travel anywhere without pain. [0 points]
- I can travel anywhere but it gives extra pain. [1 point]
- Pain is bad but I manage journeys over two hours. [2 points]
- Pain restricts me to journeys of less than one hour. [3 points]

Xpede Clinical Study

Statistical Analysis Plan

Version 1.0

Page 19 of 19

Medtronic

- Pain restricts me to short necessary journeys under 30 minutes. [4 points]
- Pain prevents me from travelling except to receive treatment. [5 points]

Total score calculation:

Now, simply add up your points for each section and plug it in to the following formula in order to calculate your level of disability: point total / 5 X Number of question checked X 100 = % disability (aka: 'point total' divided by 50 multiply by 100 = percent disability).

Possible interpretation of the total score:

- 0% to 20% (minimal disability): Patients can cope with most activities of daily living. No treatment may be indicated except for suggestions on lifting, posture, physical fitness and diet. Patients with sedentary occupations (ex. secretaries) may experience more problems than others.
- 21%-40% (moderate disability): Patients may experience more pain and problems with sitting, lifting and standing. Travel and social life are more difficult. Patients may be off work. Personal care, sleeping and sexual activity may not be grossly affected. Conservative treatment may be sufficient.
- 41%-60% (severe disability): Pain is a primary problem for these patients, but they may also be experiencing significant problems in travel, personal care, social life, sexual activity and sleep. A detailed evaluation is appropriate.
- 61%-80% (crippled): Back pain has an impact on all aspects of daily living and work. Active treatment is required.
- 81%-100%: These patients may be bed bound or exaggerating their symptoms. Careful evaluation is recommended.

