4.2. Secondary Objectives and Endpoints

The secondary endpoints include:

- Change of NRS score from baseline at 1 day and 3-month visit
- Change of ODI from baseline at 1 day, 3-month visit and 6-month visit
- Change of SF-36 from baseline at 1 day, 3-month visit and 6-month visit
- Change of Vertebral body height restoration at 1 day and 3-month visit and 6-month visit
- Change of Vertebral body Angles from baseline at 1 day, 3-month visit and 6-month visit
- Adverse events through 6-month visit. In particular, the following events will be reported:
 - Bone Cement Implantation Syndrome;
 - Bone Cement leakage;
 - Vertebral body compression fracture;
 - Adjacent vertebral body fracture;

5. Investigation Plan

The Xpede Study is a prospective, 1: 1 randomized, single blinded, multi-center human clinical trial designed to confirm the safety and efficacy profile of the Kyphon®Xpede™Bone Cement for regulatory approval in China. This study will enroll up to 180 subjects in order to demonstrate that the Kyphon®Xpede™ Bone Cement is non-inferior to the Mendec Bone Cement by more than a small pre-specified amount in terms of the primary endpoint. This amount is defined as the noninferiority margin (see section 13 from Protocol for details). Subjects will be randomly assigned with a 1:1 ratio to the Kyphon®Xpede™ Bone Cement arm or to the Mendec Bone Cement arm and then followed for a duration of 6 months in all sites. All study sites will be in China. Total duration of the study is anticipated to be approximately 12 months (6 months of enrollments and 6 months follow-up after study procedure).

Patients will be randomized 1:1 to either Xpede™ Bone Cement or Mendec bone cement. The sequence of treatments will be randomly permuted in blocks of 2 or 4 patients per block. The

Xpede Clinical Study

Statistical Analysis Plan

Version 1.0

Page 6 of 19

Medtronic

blocked randomization will be centralized and schedules will be created by the study statistician using statistical software. To minimize the selection bias, the randomization procedure for this study will use the site (3 sites), the number of vertebral to be treated (1,2 or 3) and the type of procedure (2 procedure: VP and BKP) as stratification factors, so that there will be a separate permuted block randomization list for each stratum (18). This guarantees treatment balance within strata.

[figure not shown]

Figure 1: Study Flowchart

6. Determination of Sample Size

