7.4. Handling of Missing, Unused, and Spurious Data and Dropouts

Outliers and influential observations will be identified via graphical plots and according to study team decision the analysis could be repeated excluding potential outliers.

If the proportion of missing data is less than 10% of data, data will not need a multiple imputation. It is considered that the missing data mechanisms and the missing data patterns have greater impact on research results than does the proportion of missing data when lower than 10% on this sample. In case of missing data greater than 10% and a missing pattern at random, the imputation of missing data will be performed using the most appropriate method depending on the pattern of missing in the data and the type of the imputed variable. The outcome variable will not be imputed. After the imputation of the missing values the models will be rerun.

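### SAP 10.3.3 gives two ODI scoring rules as one, but they agree only when all 10 sections are answered, and Section 8 may be skipped

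*SAP*

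**What the plan says.** SAP 4.2 lists as a secondary endpoint "Change of ODI from baseline at 1 day, 3-month visit and 6-month visit". SAP 7.9.2 models ODI across those visits with the baseline value as an explanatory variable, and refers to section 10.3 for the score.

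SAP 10.3.3 says of the instrument, "It is composed by 10 section as follow". Each section is scored from 0 to 5. One heading reads "Section 8: Sex Life (if applicable", so that section need not be answered by everyone.

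The total-score instruction at the end of 10.3.3 gives two expressions:

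- **Rule A (answered items):** "point total / 5 X Number of question checked X 100 = % disability". It is printed without brackets.
- **Rule B (fixed divisor):** the point total "divided by 50 multiply by 100 = percent disability".

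Rule B follows Rule A in a parenthesis introduced by aka, so it is offered as another name for the same calculation. Nothing limits it to questionnaires with every section answered.

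No other text settles the matter. The protocol (9.4 and 9.7) names only the ODI version. SAP 7.4 has no rule for single unanswered items; it says of outcomes only that "The outcome variable will not be imputed".

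**The concern.** The SAP provides for a questionnaire with nine answers and then gives two calculations that disagree on exactly that questionnaire. Dividing by 50 keeps the skipped section in the denominator while adding nothing to the numerator, which is the same as scoring it zero, or no disability.

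The endpoint is a change from baseline, and baseline is also a model covariate, so the choice of denominator can enter both sides of the model. A patient who answers Section 8 at one visit and not at another has a different change under each rule. If the choice is left open, it is made at programming or after data are seen, when it should have been fixed in the plan.

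**Working it through.** **Inputs, all from SAP 10.3.3**

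- Sections: 10.
- Maximum per section: 5 points; for Section 8 the top response is "Pain prevents any sex life at all. [5 points".
- Section that may be left out: Section 8, leaving k = 9 answered and a maximum of 45 points.
- Rule A, with the brackets it needs: A = 100 × T / (5 × k), where T is the point total.
- Rule B: B = 100 × T / 50.

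**Step 1. The SAP's own equivalence.** With k = 10, 5 × 10 = 50, so A = B for every T from 0 to 50. The stated equivalence is reproduced for complete questionnaires.

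**Step 2. Section 8 skipped.** With k = 9, A = 100 × T / 45 and B = 100 × T / 50, so B / A = 45 / 50 = 0.90.

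| T (nine sections) | Rule A | Rule B | Gap (points) |
|---|---|---|---|
| 0 | 0% | 0% | 0 |
| 9 | 20% | 18% | 2 |
| 18 | 40% | 36% | 4 |
| 27 | 60% | 54% | 6 |
| 36 | 80% | 72% | 8 |
| 45 | 100% | 90% | 10 |

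Under Rule B the highest attainable score is 90%. Some totals also move to a lower interpretation band of the SAP: T = 28 is 62.2% under A (the 61–80% band) and 56.0% under B (the 41–60% band).

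**Step 3. Change from baseline**

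| Section 8 | Baseline | Follow-up | Change, Rule A | Change, Rule B |
|---|---|---|---|---|
| Skipped at both visits | 30 of 45 | 12 of 45 | −40 | −36 |
| Skipped at baseline only | 27 of 45 | 20 of 50 | 60% to 40% = −20 | 54% to 40% = −14 |
| Skipped at follow-up only | 30 of 50 | 18 of 45 | 60% to 40% = −20 | 60% to 36% = −24 |

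When one visit is incomplete, the two changes differ by 10% of the Rule A score at that visit: 4 points at 40%, 6 at 60%, 8 at 80%. Rule B shows less improvement when the gap is at baseline and more when it is at follow-up.

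**Step 4. Effect on a group mean.** The documents give no skip rate, so this is an assumption: a share s skips Section 8 at both visits, and skipping is unrelated to score. The mean change under Rule B is then (1 − s) + 0.90 × s = 1 − 0.10 × s times that under Rule A.

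| s | Shrinkage of mean change |
|---|---|
| 10% | 1% |
| 50% | 5% |
| 100% | 10% |

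**Step 5. The missing brackets.** Read strictly left to right, Rule A for 27 points on nine sections gives 27 / 5 × 9 × 100 = 4,860.

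**The case against.** The strongest reply is that Rule A comes first and is the general rule, and that the 50 in parentheses is only its value for a complete ten-section form. On that reading nothing is wrong. A reader might infer that the SAP commits the trial to understating disability. The documents do not support that: the understatement arises only if Rule B is the version programmed, and only when the total is above zero. What remains is that the SAP equates the two rules without limiting the second to complete forms, while itself allowing an incomplete one.

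A reader might also take the 4 to 8 points as error against a known true score. It is not. Rule A assumes that the skipped section would have scored the average of the other nine. With 27 points on nine sections, a Section 8 score of 5 would give 32/50 = 64%; a score of 0 would give 27/50 = 54%, which is the Rule B value. The figure is the difference between the two rules. Rule A can itself produce a change when Section 8 is answered at one visit only.

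The missing brackets carry little practical risk. SAP 10.3.3 interprets scores on a 0–100% scale, so 4,860 would be noticed at once.

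The validation section of the SAP (section 8) requires double programming and review by a second statistician. That would tend to expose two programmers who chose different denominators. It would not say which was intended, and it would flag nothing if both chose 50.

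Finally, the same rule applies to both arms, and randomisation should make the share of skipped sections similar on average. That limits any distortion of the comparison between arms but does not settle how the score is computed.

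**Conclusion.** The point holds as an inconsistency in a stated scoring rule. SAP 10.3.3 treats as equivalent two formulas that differ whenever a section is unanswered and the total exceeds zero, and Section 8 is expected to go unanswered by some patients. If Rule B is used for those patients, each such score is 90% of the answered-items score, a gap of up to 10 points. With one incomplete visit, the change differs between rules by about 4 to 8 points for answered-items scores of 40% to 80%, in either direction.

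The effect on group means cannot be known from the documents. Under the stated assumption on s it is about 10% × s, so 1% at s = 10% and 5% at s = 50%.

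A reader might infer a threat to the trial's main conclusion. There is none: ODI is secondary with no margin or success criterion, and success rests only on the NRS and vertebral body angle endpoints (SAP 7.9.1). Neither those endpoints nor the sample size is affected. The point is worth correcting because the rule defines a pre-specified endpoint at three visits and, followed as the divide-by-50 version, scores an inapplicable section as no disability.

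**What to change.** In SAP 10.3.3, replace the total-score instruction with one bracketed rule:

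ODI % = 100 × point total / (5 × number of sections answered)

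Delete the divisor of 50, or state that it applies only when all 10 sections are answered. While editing, the sponsor could also set a minimum number of answered sections below which no score is computed; that is a useful addition, not needed to resolve the conflict.

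The cost is a one-line SAP change, with no effect on data collection, sample size or the primary analyses. It should be made before the ODI data are analysed, so that the denominator is not chosen afterwards.
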